4.5.6 Malignancies

Malignancy and pre-malignancy AEs will be identified using the SMQ of “Malignant tumours (narrow)” and “Pre-malignant disorders,” respectively.

The number of patients with a malignancy and serious malignancy will be summarized by SOC and PT. The pre-malignancy AEs will be listed.

The rate per 100 patient-years by treatment group (along with the 95% CI) will be calculated for malignancies.

4.5.7 Multiple Sclerosis Relapses

For clinically reported relapses, the number and percentage of patients experiencing an event will be summarized.

4.5.8 Pregnancies

Pregnancy information will be summarized in individual patient listings.

4.5.9 Magnetic Resonance Imaging Data

Non-MS pathology reported by the local safety radiologist on the CRF will be listed by treatment arm.

4.5.10 Laboratory Data

Abnormal laboratory outcomes will be reported. A summary of the number and percentage of patients with abnormal laboratory outcomes, along with each grade by laboratory parameter, will be summarized by treatment group for all laboratory assessments.

The absolute values and changes from baseline at each visit will be summarized for all laboratory assessments, including those for hematology, chemistry, immunoglobulins (IgA, IgM, IgG) and T-cell subtype (CD3, CD4, CD8).

For the liver laboratory parameters, the number and percentage of patients with an elevated post-baseline Aspartate aminotransferase (AST) or Alanine Transaminase (ALT) level will be summarized by treatment.

The association of decrease in each immunoglobulin (IgA, IgM, IgG) and serious infections will be investigated by reporting the incidence rate of serious infections per 100 patient year during the episodes of confirmed drop of immunoglobulin levels below lower limit of normal (LLN) versus the incidence rate of serious infections per 100 patient year in the remaining exposure (before or after a confirmed drop, and during the overall exposure for the patients without any confirmed drop of immunoglobulin) for each treatment arm. The exposure of a confirmed episode is counted from the day the immunoglobulin first decreased below LLN until the day it is normalized above LLN, and

the serious infections with onset date in between are counted. The 95% CI will be calculated using Poisson distribution methods.

The association of decrease in each T-cell subtype (CD3, CD4, CD8) and serious infections will also be investigated.

Immunoglobulins

The median immunoglobulin levels (IgA, IgG, IgM, and total Ig) will be displayed graphically over time from the first infusion of study drug. Absolute values, changes from baseline, and percent changes from baseline will be summarized over time. At each time point, the number and percentage of patients with immunoglobulin levels lower than the lower limit of normal will be presented.

HBV DNA

Hepatitis B virus (HBV) DNA (polymerase chain reaction [PCR]) in patients who enrolled with negative hepatitis B surface antigen (HBsAg) and positive total hepatitis B core antibody (HBcAb) will be listed.

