6.5 SAFETY ANALYSES

The safety analysis population will consist of all randomized patients who received at least one infusion (partial or complete) of study drug (ocrelizumab or placebo), with patients grouped according to treatment received.

All verbatim adverse event terms will be mapped to MedDRA thesaurus terms, and adverse event severity will be graded according to NCI CTCAE v5.0.

The main safety objective for this study is to evaluate the safety of ocrelizumab compared with placebo until when patients receive any PDP OCR, commercial ocrelizumab treatment, or other MS DMT in all patients who receive at least one infusion (partial or complete) of study drug (ocrelizumab or placebo).

The safety endpoints considered are as follows:

- Adverse events leading to study treatment withdrawal
- Adverse events in patients previously treated with an another DMT for MS
- Proportion of patients with adverse events and serious adverse events
- Incidence rates per 100 PY for infections, serious infections, death, and malignancies, including breast cancer
- Vital signs (blood pressure and pulse rate) during and 1 hour after infusion
- Change from baseline in laboratory test results for hematology and chemistry
- Change from baseline in laboratory test results for immunoglobulins (IgA, IgM, IgG) and T-cell subtype (CD3, CD4, CD8): MMRM analyses will be performed. Fixed effects in the model will include treatment arm, visit, treatment by visit interaction, stratification factors, baseline value of the immunoglobulin or T-cell, and baseline by visit interaction. Visits will be treated as a repeated variable within a patient. Patient, treatment, and visit will be treated as factor variables. An unstructured variance-covariance structure will be applied to model the within-patient errors. Appropriate variance stabilizing transformations of the laboratory measurements (e.g., log-transformation) may be applied.

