1. INTRODUCTION

Study WA40404 is a Phase IIIb, multicenter, randomized, double-blind, placebo-controlled study to evaluate the efficacy and safety of ocrelizumab compared with placebo in patients with primary progressive multiple sclerosis (PPMS), including patients later in their disease course.

Ocrelizumab is a recombinant humanized, glycosylated, monoclonal IgG1 antibody that selectively targets and depletes cluster of differentiation (CD) 20-expressing B cells, while preserving the capacity of B-cell reconstitution and preexisting humoral immunity. CD20 is a B-cell surface molecule that is restricted in expression to pre-B cells and mature B cells but is not expressed earlier in the development of B cells (Banchereau and Rousset 1992). Based on the results of ocrelizumab Phase III studies in patient populations with relapsing multiple sclerosis (RMS) and PPMS, ocrelizumab was approved by the United States Food and Drug Administration (FDA) on 28 March 2017 for the treatment of adult patients with RMS and PPMS and by the European Medicines Agency (EMA) on 12 January 2018 for patients with active relapsing forms of multiple sclerosis (MS) defined by clinical or imaging features and for patients with early PPMS in terms of disease duration and level of disability, and with imaging features characteristic of inflammatory activity.

The background for the study can be found in the study protocol.

The analyses described in this Statistical Analysis Plan (SAP) will supersede those specified in Protocol WA40404.

Changes to the protocol-planned analyses are described in Section 4.8.

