4.8 CHANGES TO PROTOCOL-PLANNED ANALYSES

The endpoint Annual rate of percent change from baseline in total volume of T2 lesions was changed to the endpoint Annual rate of change from baseline in radius of total volume of T2 lesions.

The endpoint Annual rate of percent change from baseline in total non-enhancing T1 lesion volume on MRI scan of the brain was changed to the endpoint Annual rate of change from baseline in radius of total non-enhancing T1 lesion volume on MRI scan of the brain.

The rationale for not considering the percent change from baseline is that certain patients might have zero lesions at baseline, in which case the percent change from baseline would be non-estimable. Moreover, the percent change from baseline in lesion could be highly skewed due to very small baseline values and hence would not follow a normal distribution. The radius transformation is applied as the RCRM model for the analysis relies on a normality assumption.

[figure not shown]

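### The SAP omits the protocol's MMRM for immunoglobulin and T-cell change without listing the omission, so this safety comparison has no adjusted arm difference with a confidence interval

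*SAP*

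**What the plan says.** Under the main safety objective, Protocol Section 6.5 states: "Change from baseline in laboratory test results for immunoglobulins (IgA, IgM, IgG) and T-cell subtype (CD3, CD4, CD8): MMRM analyses will be performed". It then gives the model: "Fixed effects in the model will include treatment arm, visit, treatment by visit interaction, stratification factors, baseline value of the immunoglobulin or T-cell", plus a baseline-by-visit interaction. On covariance it adds: "An unstructured variance-covariance structure will be applied to model the within-patient errors". A variance-stabilising transformation, such as the logarithm, is allowed.

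SAP Section 4.5.10 covers the same parameters in one general sentence: "The absolute values and changes from baseline at each visit will be summarized for all laboratory assessments, including those for hematology, chemistry, immunoglobulins" (the sentence goes on to name IgA, IgM, IgG, CD3, CD4 and CD8). For immunoglobulins it adds a plot of medians, the percentage of patients below the lower limit of normal (LLN) at each time point, and this: "Absolute values, changes from baseline, and percent changes from baseline will be summarized over time". It names no model for any laboratory parameter.

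The SAP Introduction says that its analyses supersede those in the protocol and that "Changes to the protocol-planned analyses are described in Section 4.8". Section 4.8 records two changes. The first begins "The endpoint Annual rate of percent change from baseline in total volume of T2 lesions was changed". The second is the corresponding change for non-enhancing T1 lesion volume. No laboratory analysis is mentioned.

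**The concern.** A reader who relies on Section 4.8 would conclude that the protocol's laboratory analyses stand, when the modelled one has gone. The parameters are not routine. Protocol Section 5.1.1.1 lists immunoglobulin decrease among the identified risks, says that the proportion below LLN rose over time and with successive dosing, and reports an observed association with serious infections that was clearest for IgG. SAP Table 3 makes change in immunoglobulin levels an endpoint of the main safety objective, which compares ocrelizumab with placebo.

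Two things are lost with the model. One is an arm difference adjusted for baseline and stratification factors, with a confidence interval. The other is the use of earlier values from patients with no value at a late visit. A by-visit table uses only the values present at that visit.

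**Working it through.** There is no sample size, power or alpha figure to reproduce. The check is a comparison of texts, followed by a rough gauge of scale.

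**1. Is the model elsewhere in the SAP?** No. The SAP's only MMRM is in Section 4.4.1, for continuous eCOA endpoints (MFIS, ABILHAND, Neuro-QoL-UE, MSIS-29 physical, SDMT). By contrast, the neighbouring protocol item, serious infection rates during confirmed immunoglobulin falls, was carried into SAP Section 4.5.10 almost unchanged.

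**2. What remains and what is missing?**
- Remaining for all six parameters: absolute values, changes from baseline and graded abnormalities.
- Remaining for immunoglobulins only: percent changes, median plots and percentage below LLN.
- Missing: adjustment for baseline, baseline by visit and stratification factors; an arm difference with a confidence interval; and any stated handling of missing laboratory values. That the summaries use observed values only is inferred from this silence.

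**3. How many values could be missing?** The inputs are the 10% annual dropout in SAP Section 2.2 and the immunoglobulin visits in Protocol Appendix 1, the last of which falls at Week 132.
- t = 132 × 7 / 365.25 = 2.53 years.
- 1 − 0.9^2.53 = 0.234, and 1 − exp(−0.10 × 2.53) = 0.224.

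So about 22% to 23% of patients could be gone by then. The same formulas give about 9% at Week 48 and 24% to 25% at Week 144.

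**4. When would the missing values matter?** All inputs here are assumed, because the documents give no immunoglobulin trajectory.
- *Dropout depends on level.* Assume 500 patients in an arm, a true change of −0.60 baseline SD, and individual slopes drawn independently of baseline and varying little. With log-odds of dropout of 0, 0.5 and 1.0 per SD lower level, the last-visit mean minus the full baseline mean was −0.60, −0.44 and −0.25. The paired change from baseline stayed at −0.60, as did an MMRM-type likelihood estimate.
- *Dropout depends on the fall itself.* Assume IgG of 10 g/L at baseline (SD 2.2) and a mean slope of −0.4 g/L per year. The true change at Week 132 was about −1.02 g/L. Observed-value means were −0.94, −0.87 and −0.63 when the dropout hazard rose by 28%, 65% and 172% per extra 1 g/L fall. The likelihood estimate stayed at −1.01 to −1.02. With no such dependence there was no bias.

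Absolute levels can therefore be distorted if dropout depends on level. By the same reasoning so can the percentage below LLN, which was not simulated. Changes from baseline are distorted only if dropout depends on the change, directly or because level and change are correlated.

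**5. What does baseline adjustment gain?** With equal variances and baseline correlation r, the variance of the adjusted arm difference relative to that of change scores is 2(1 − r) → (1 − r²), a ratio of (1 + r)/2. This is 0.95 at r = 0.9 and 0.85 at r = 0.7, a reduction of 5% to 15%.

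**The case against.** The strongest reply is that the SAP may do this and that little is lost. Protocol Section 6 calls its statistical text a summary and gives the SAP precedence. The outputs closest to patient risk stay in Section 4.5.10: percentage below LLN, graded abnormalities, and serious infection rates during confirmed immunoglobulin falls. For the long-term ocrelizumab pool, Protocol Section 6.5 lists change in immunoglobulins without an MMRM, so restoring the model affects only the placebo-controlled period.

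A reader might also infer that the tables will understate the decline because low IgG blocks re-treatment and so removes the worst-affected patients. The documents do not support that chain:
- Protocol Section 4.3.2.3 suspends drug administration, not sampling.
- Patients who stop treatment move to Follow-Up 1, where Appendix 2 still schedules immunoglobulins and flow cytometry every 12 weeks.
- Under SAP Section 4.5 the safety window closes at PDP OCR, OLE OCR, commercial ocrelizumab or another MS DMT, not at treatment withdrawal.
- Under Protocol Section 4.2 immunoglobulin levels are blinded until the primary analysis, apart from reflex messages for abnormal results. A dropout hazard that rises smoothly with each 1 g/L fall is hard to square with that.
- On the assumed IgG distribution (mean 10 − 1.02 = 8.98, SD 2.2 to 2.6), only about 0.5% to 1.5% of patients would be under the 3.3 g/L re-treatment threshold at Week 132 (z = −2.58 to −2.18).

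All of this stands, and it confines the bias argument to a possibility. It does not supply the missing arm comparison. Precedence lets the SAP change the analysis, but the SAP itself says that changes are described in Section 4.8, and this one is not.

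**Conclusion.** The discrepancy is certain on the text: a fully specified protocol analysis is absent from the superseding SAP and from its list of changes. The consequence is that the main placebo-controlled comparison of immunoglobulin and T-cell change has no covariate-adjusted arm difference with a confidence interval. The precision forgone is modest, 5% to 15% of variance under the assumed correlations.

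Bias in the late-visit tables is possible but not shown. It needs dropout related to the immunoglobulin level or its change, and every simulated figure rests on assumed inputs. The model's advantage in turn assumes that values are missing at random given the earlier ones.

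Two stronger readings should be resisted. Baseline is not ignored, because changes from baseline are still tabulated; what is lost is covariate adjustment. Nor do the documents show whether the model was dropped deliberately or by oversight. Alpha, power and every efficacy result are untouched. This is worth correcting before database lock but does not threaten the trial's main conclusions.

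**What to change.** In SAP Section 4.5.10, reinstate the Protocol Section 6.5 MMRM for IgA, IgM, IgG, CD3, CD4 and CD8. Apply it to the safety analysis set over the placebo-controlled window already defined in SAP Section 4.5, with log transformation if needed. Report the adjusted mean change per arm and the arm difference with its 95% confidence interval at each visit scheduled for that parameter. Keep the descriptive tables as support.

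If the removal is deliberate, list and justify it in Section 4.8 and state how missing laboratory values are handled.

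The cost is SAP wording and the programming of a standard model that the protocol already specifies. No new data are needed.

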3.1.1.4 Follow-Up 1 Phase

All patients who discontinue prematurely from the double-blind treatment phase will enter the FU1 phase, including patients who receive other DMTs for MS, commercial ocrelizumab, or no treatment. The FU1 phase will run in parallel with the double-blind treatment phase until 144 weeks from randomization for each patient *or until the primary analysis, whichever occurs earlier*. Scheduled visits will be performed every 12 weeks analogically to the initial (double-blind) schedule of activities and will include both efficacy and safety assessments (see [Appendix 2](#)). In the FU1 phase, patients will remain blinded to their original (randomized) treatment assignment. Patients who withdraw from treatment should be encouraged to remain in the study for the full duration of the FU1 phase. All patients who are ongoing in the FU1 phase at 144 weeks from randomization for each patient *or at the time of the primary analysis* will continue in the FU2 phase (see Section [3.1.1.6](#)).

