- Association of decrease in each immunoglobulin (IgA, IgM, IgG) and serious infections: incidence rate of serious infections per 100 PY during the episodes of confirmed drop of immunoglobulin levels below LLN versus the incidence rate of serious infections per 100 PY in the remaining exposure (before or after a confirmed drop, and during the overall exposure for the patients without any confirmed drop of immunoglobulin) for each treatment arm. The exposure of a confirmed episode is counted from the day the immunoglobulin first decreased below LLN until the day it is normalized above LLN, and the serious infections with onset date in between are counted. The 95% confidence interval will be calculated using Poisson distribution methods.
- Association of decrease in each T-cell subtype (CD3, CD4, CD8) and serious infections will be analyzed as for the immunoglobulin described above.

Additional safety objectives for this study will include evaluation of the following:

- Subgroup analyses: patients with MRI-active versus MRI-inactive, patients aged ≤ 55 versus > 55 years, patients with a baseline EDSS score of ≤ 6.5 versus > 6.5 , females and males, and patients previously treated (prior to randomization) with another DMT for MS
- Incidence rates per 100 PY for infections, serious infections, death, and malignancies, including breast cancer
- Pharmacodynamics, as measured by B-cell levels in blood

The ocrelizumab pool for long-term safety analysis will consist of all randomized patients who received at least one infusion (partial or complete) of ocrelizumab (study drug, PDP OCR, or commercial ocrelizumab) until when patients receive any other MS DMT as follows:

- Adverse events leading to withdrawal of ocrelizumab treatment
- Adverse events in patients previously treated with another DMT for MS
- Proportion of patients with adverse events and serious adverse events
- Incidence rates per 100 PY for infections, serious infections, death, and malignancies, including breast cancer
- Change from first administration of ocrelizumab in laboratory test results for hematology and chemistry
- Change from first dose of ocrelizumab in immunoglobulins (IgA, IgM, IgG) and T-cell subtype (CD3, CD4, CD8)
- Associations of decrease in each immunoglobulin (IgA, IgM, IgG) and serious infections
- Associations of decrease in each T-cell subtype (CD3, CD4, CD8) and serious infections

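### Low-immunoglobulin time is back-dated to the first low sample but counts only if later confirmed, so a serious infection that ends observation before another sample is classed as not low

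*SAP*

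**What the plan says.** SAP 4.5.10 (Laboratory Data) relates falls in IgA, IgM and IgG to serious infections by comparing two rates per 100 patient-years within each arm. The first is the rate "during the episodes of confirmed drop of immunoglobulin levels below lower limit of normal (LLN"). The second is the rate in the remaining exposure: "before or after a confirmed drop, and during the overall exposure for the patients without any confirmed drop of immunoglobulin". An episode's exposure is "counted from the day the immunoglobulin first decreased below LLN until the day it is normalized above LLN". An infection is attributed to an episode by when it began: "the serious infections with onset date in between are counted". Protocol 6.5 has the same rule ("The exposure of a confirmed episode is counted from the day the immunoglobulin first decreased below LLN") and extends it to CD3, CD4 and CD8. The SAP, which supersedes the protocol, says only that the T-cell association will also be investigated.

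Neither document says what makes a drop confirmed, how far apart the two values must be, which visits may supply the confirming value, or how a low value with no later sample is handled.

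Immunoglobulin sampling, from the schedules of activities:

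- **Double-blind (Appendix 1):** screening, Weeks 0, 12, 36, 60 and 84, then 12 weeks after each later dose (Weeks 108 and 132), and the treatment discontinuation visit. None is marked at the dosing visits after Week 0, or at delayed-dosing or unscheduled visits.
- **FU1 (Appendix 2):** each follow-up visit. Protocol 3.1.1.4 says "Scheduled visits will be performed every 12 weeks analogically to the initial (double-blind) schedule of activities". None is marked at the end-of-observation or withdrawal-from-follow-up visit.
- **OLE (Appendix 3):** OLE screening, 1 to 30 days before OLE Week 0.
- **FU2 (Appendix 4):** the Week 24 visit.

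**The concern.** Time after a first low value is classified with information that arrives later. For that interval to count as low, the patient must stay under observation until another sample is drawn. Patients who get there bring the whole interval into the low group. Patients whose infection ends observation first take the infection, and the time leading to it, into the comparator. This is immortal-time misclassification. For the affected cases it runs one way: events leave the low-immunoglobulin numerator and enter the comparator's.

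Two patients show it. Both have a first low IgG at Week 36 and a serious infection at Week 50. One recovers and is low again at Week 60, so the infection counts as low. The other dies of the infection, so the infection and the 14 weeks since the low sample (50 − 36) count as not low.

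Protocol 5.1.1.1 reports that an association between falling immunoglobulins and serious infections has already been seen with ocrelizumab, most clearly for IgG. This analysis examines that signal, and the rule can drop the gravest infections from the group under study.

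**Working it through.** The plan gives no figure to reproduce. The check has three steps.

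**1. Unconfirmed window.** The inputs are the Appendix 1 sampling weeks and the 144-week double-blind phase. For a patient who stays low, share = (weeks to next scheduled double-blind sample) ÷ (144 − week of first low).

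| First low (week) | Next sample (week) | Window ÷ low time to Week 144 | Share |
|---|---|---|---|
| 12 | 36 | 24 ÷ 132 | 18% |
| 36 | 60 | 24 ÷ 108 | 22% |
| 60 | 84 | 24 ÷ 84 | 29% |
| 84 | 108 | 24 ÷ 60 | 40% |
| 108 | 132 | 24 ÷ 36 | 67% |
| 132 | none in this schedule | 12 ÷ 12 | 100% |

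The scheduled gap is 24 weeks from Week 12 on; the first gap is 12 weeks. The Week 132 row stops at the double-blind schedule and ignores OLE-screening and FU2 samples.

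**2. Infections moved.** Let f be the share of serious infections that end observation with no further immunoglobulin sample. At a constant infection rate, the share of low-immunoglobulin infections moved to the comparator is about f × the share above. With f = 10%, that is 1.8% (first low at Week 12) to 10% (Week 132). With f = 30%, it is 5.5% to 30%.

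**3. Effect on the rate ratio, by simulation.** None of these inputs comes from the documents: 3 serious infections per 100 patient-years; 30% of patients become persistently low, with onset uniform over 0 to 144 weeks; double-blind samples only; one infection per patient. Entries are the estimated low/not-low rate ratios.

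| f | True 1: from first low | True 1: confirmed | True 2: from first low | True 2: confirmed |
|---|---|---|---|---|
| 0% | 0.98 | 0.98 | 1.85 | 1.85 |
| 5% | 0.97 | 0.96 | 1.87 | 1.82 |
| 10% | 0.98 | 0.94 | 1.87 | 1.79 |
| 30% | 0.98 | 0.88 | 1.89 | 1.66 |
| 100% | 0.99 | 0.66 | 1.95 | 1.24 |

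Counting from the first low value stays a little under 2 because low time before the first low sample is still classed as not low. At f = 0 the two rules agree, so the gap between them comes from infections that end observation.

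Counting without confirmation has its own cost. If 2 to 5% of samples are isolated low values, the time-updated ratio falls to about 1.7 to 1.85 when the truth is 2, and stays close to 1 when the truth is 1. At f of 5 to 10%, neither rule is clearly the more accurate.

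**The case against.** The strongest reply is that few patients can be affected, and most of it stands.

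- A reader might infer that anyone who stops treatment after a serious infection is lost to the low group. The schedules do not support that: the treatment discontinuation visit and the 12-weekly FU1 visits both include immunoglobulins. The error needs death, or study withdrawal without a further sample.
- A reader might infer from Appendix 1 that a first low value at Week 132 can never be confirmed. OLE screening falls just before the first OLE dose, and patients who do not enter the OLE are sampled in FU2. What remains is that the plan does not say whether such samples may confirm. The FU2 sample also falls after the DBT/FU1 observation period defined in SAP 4.5.1.2.
- The planned 10% annual dropout does not measure the bias. Dropout unrelated to infection causes no material distortion, as the f = 0 row shows.
- The 24-week gap should not be carried over to CD4. Appendix 1 draws it at the dosing visits with flow cytometry and again between them, about every 12 weeks.
- This is a descriptive summary with Poisson intervals and no hypothesis test. SAP 4.5.2 lists all deaths, SAP 4.5.4 lists serious infections, and SAP 4.5.10 shows the proportion below LLN over time. A fatal infection after a low value would be visible elsewhere, though not in this comparison.

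These points limit the reach and size. They do not supply the missing definition or remove the dependence on a later sample.

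**Conclusion.** The point holds in limited form. A back-dated start, a confirmation requirement and a comparator that absorbs all unconfirmed time together bias the association downward for serious infections that end observation before another immunoglobulin sample. This assumes that confirmation means a later low sample, which is the natural reading but is not stated.

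On the assumed inputs, with a true ratio of 2, the loss is small if 5 to 10% of serious infections end observation this way (1.82 to 1.79, against 1.87). It is visible at 30% (1.66 against 1.89) and large only at the extreme of 100% (1.24 against 1.95), the situation of an analysis restricted to fatal infections. The documents give no figure for this share. Because the simulation uses double-blind samples only, it leaves out confirmation from treatment-discontinuation, FU1, OLE-screening and FU2 samples.

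A reader might go further and conclude that the plan conceals the known IgG signal. The documents do not support that: the likely effect is modest, and the individual cases are listed. The case for change is that a safety classification rests on an undefined term and that the remedy is cheap.

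**What to change.** In SAP 4.5.10:

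1. Add a time-updated analysis and report it beside the confirmed-episode version. Low time runs from each sample below LLN to the next sample at or above LLN, or to the end of observation if there is none, with no confirmation required.
2. Define confirmation, including any minimum interval, and state that any later study immunoglobulin sample may confirm, including treatment-discontinuation, FU1, OLE-screening and FU2 samples.
3. Do not patch the rule by treating only a final low value as confirmed. A single low value would then count when the patient dies, but not when a survivor's next value is normal. That depends on the outcome and biases toward an association.

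If the Protocol 6.5 method is kept for T cells, say so in the SAP and apply the same definitions, using each marker's own sampling schedule.

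The cost is SAP wording and minor programming, with no new samples. The downside is that isolated low values enter the time-updated analysis and dilute it somewhat, which is why both versions should be shown.
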